## 2.1.3. Use of Connected Devices for Insulin Management

Smart insulin pens can provide the missing data to allow HCPs and PwD to inform optimised insulin treatment decisions (Adolfsson et al. 2020; Heinemann et al. 2021; Klonoff and Kerr 2018; Kompala and Neinstein 2021; Munshi et al. 2019, Sy et al. 2022). Recent American Association of Clinical Endocrinology (AACE) guidelines recommend that the use of connected pens may help patients with diabetes and clinicians:

- optimise insulin regimens, and
- avoid stacking of rapid acting insulin, which may lead to hypoglycaemia (Grunberger et al. 2021).

Studies with connected insulin pens have allowed HCPs to identify more precisely the frequency of MBDs in groups of people with T1D and T2D on CGM (Edwards et al. 2021; Adolfsson et al. 2020; Munschi et al. 2019, Gomez-Peralta et al. 2023).

Adolfsson et al. (2020) evaluated the use of a reusable insulin connected pen in the setting of a prospective multicentre observational study in Sweden, in 94 people with T1D using CGM. During the "baseline" observation period with blinded CGM, at least 25% of meals had a missed dose on average, assuming 3 meals per day. This amounted to 5 meals with a missed dose per week on average. Over an average period of 7 months, the authors could show an improvement of almost 2 hours in TIR (70-180 mg/dL), mainly due to a reduction of time above range (TAR) (>180 mg/dL). This happened thanks to an improvement of adherence to insulin therapy with 43% fewer MBDs (N = 14 patients).

Despite the low sample size, this suggests that evaluating past dosing data together with HCPs may have helped participants to remember and administer their mealtime doses, or to improve the timing of the dose, relative to the meal. The data is consistent with the hypothesis that connected pens may support people with the management of their insulin treatment regimens and help reduce missed and mistimed bolus doses.

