1.1. Objectives and Endpoints

Objectives	Endpoints		
Primary			
To compare the number of missed bolus doses (MBDs) during the last weeks of the unmasked Study Period 2 (Weeks 15 to 18), compared to the last weeks of the masked Study Period 1 (Weeks 5 and 6) in participants using the • Humalog® Tempo TM Pen • Tempo Smart Button TM • Glooko® Research Mobile Application (RMA), and Dexcom G6 Continuous Glucose Monitoring (CGM) system.	Difference in the average number of MBDs per week in the masked versus unmasked portions of the study. MBD is defined as no insulin dose from 1 hour prior to through 1 hour after the start of a glucose excursion (meal), where a glucose excursion is defined as a >70 mg/dL (>3.9 mmol/L) rise within 2 hours, not preceded by a value <70 mg/dL (<3.9 mmol/L).		
Secondary			
 To evaluate difference in participant CGM time in range (TIR) (≥70 mg/dL to 180 mg/dL) in Study Period 1 versus Study Period 2. To evaluate difference in participant CGM time above range (TAR) (>180 mg/dL and >250 mg/dL) in Study Period 1 versus Study Period 2. 	 CGM TIR (≥70 mg/dL to 180 mg/dL) in the masked versus unmasked portions of the study CGM TAR (>180 mg/dL and >250 mg/dL) in the masked versus unmasked portions of the study CGM TBR (54 mg/dL ≤ TBR < 70 mg/dL and <54 mg/dL) in the masked versus unmasked portions of the study 		

Objectives

- To evaluate difference in participant CGM time below range (TBR) (54 mg/dL ≤ TBR < 70 mg/dL and <54 mg/dL) in Study Period 1 versus Study Period 2.
- To evaluate Coefficient of Variation and mean sensor glucose from CGM values in Study Period 1 versus Study Period 2.
- To examine occurrence and change in frequency of mistimed boluses per week between Study Period 1 versus Study Period 2.
- To evaluate the change in total insulin doses (basal, mealtime per meal type, and correction bolus) between Study Period 1 versus Study Period 2.
- To evaluate occurrence, change and Study Period 1 versus Study Period 2 change in correction boluses.
- To examine the association between MBD and TIR, TAR, TBR, and HbA1c
- To examine the association between mistimed bolus and TIR, TAR, TBR, HbA1c.
- To assess device preference, satisfaction, convenience, and ease of use.

Endpoints

- Coefficient of variation and mean sensor glucose from CGM data collected from each participant
- Occurrence and change of mistimed boluses

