4.3.1. Definition of Endpoints

4.3.1.1. Missed Bolus Doses

MBDs will be identified by using the CGM (interstitial glucose values) and Tempo Smart Button data.

MBD is defined as no insulin dose from 1 hour prior to through 1 hour after the start of a glucose excursion, where a glucose excursion is defined as a >70 mg/dL (>3.9 mmol/L) rise within 2

hours, not preceded by a value <70 mg/dL (<3.9 mmol/L) (Edwards et al. 2022). If a dose between 1000 and 1100 hours would be classified as the correct or optimum time to administer the insulin dose before the 1100 hour meal, no insulin dose between 1000 and 1200 hours would be an MBD (Figure 4.1).

Abbreviation: MBD = missed bolus dose.

[figure not shown]
Figure 4.1. Missed bolus dose.

The Algorithm for identifying MBDs for each participant is as follows. Note that the algorithm will be applied to determine its adequacy, no adjustment of the algorithm will be made after the database lock.

- 1. Identify all the nadirs (Nt, t = 1, to m, m = the count of the last nadir) in the analysis period. The missed dose identification procedure starts from t = 1.
- 2. Identify missing doses associated with the nadirs:
 - i. If an increase of 70 mg/dL or more from Nt is NOT found prior or at minimum (Nt + 2 hours, Nt+1), then move to the next nadir and repeat Step 2 (no excursion occurred post Nt and prior to next nadir or Nt + 2 hours, whichever is closer to Nt),
 - ii. If an increase of 70 mg/dL or more from Nt is found prior or at minimum (Nt + 2 hours, Nt+1), then Pen data will be examined.
 - a) If there is an injection within 1 hour prior to Nt, then move to the next nadir and repeat step 2,
 - b) If there is NO injection found within 1 hour prior to Nt, and if the 70 mg/dL increase is prior to an injection after the Nt, or if there is an injection before reaching the 70 mg/dL increase but over 30 minutes after the Nt, then the number of missed dose + 1 and move to the next nadir and repeat Step 2,
- 3. Step 2 will be repeated until the end of the analysis period.

The definitions and clarification of the terms used in the algorithm:

[figure not shown]

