- 1. **Nadir**: a nadir is defined as the time-point (Nt) with the lowest glucose in the time window from Nt 30 minutes to Nt + 30 minutes, inclusive (in other words, 30 minutes prior to the time-point to 30 minutes post the time-point). The first and the last nadir in the analysis period might have fewer readings prior or post the nadir respectively. The nadir must not be preceded by a hypoglycemia (<70 mg/dL) (Figure 4.2).
 - If there are 2 or more tied nadirs identified within 30 minutes, the last nadir will be the nadir in the time window.
- 2. **Date and time of injection**: among the several records (within seconds or minutes, but not more than 30 minutes) captured for each injection in the Pen data, the date and time of the last record will be used for the injection in the calculation.
- 3. **Analysis period:** the period with consecutive CGM readings (every 5 minutes) without more than 2 hours gap.
 - If the gap is more than 2 hours, a new analysis period will start from the first reading post the gap to the next gap/end of the study period. The identification will be performed in the analysis period if the duration of the analysis period is more than 2 hours, but will not be done otherwise.
- 4. Algorithm will be applied in the analysis period based on available data, without missing data imputation (in other words, the time-points with missing data will not be taken into account). However, the values of "High" and "Low" will be replaced by 401 and 39 respectively, since the CGM platform cannot provide the actual results once the glucose levels are over 400 or under 40. Any value above 400 will be reset to 401 and any value under 40 will be reset to 39 if there are any such readings.

* This condition means that the glucose levels 30 minutes before and 30 minutes after are not larger than the current (G_t)

* The check for increase in the diagram would be of 70 mg/dL.

Figure 4.2. Nadir identification diagram.

The check for increase in the diagram would be of 70 mg/dL.

Figure 4.3. Missed bolus dose identification diagram.

Based on the results of the missed bolus doses, the number of days per week with a missed bolus dose for each participant will be estimated.

For each participant the number of missed bolus doses per week in the period will be calculated using the formula:

(Total number of Missed Bolus doses / Number of Days with Evaluable CGM data) * 7

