4.4.1.1.6. Occurrence and Change in Mistimed Bolus Doses Frequency

Mistimed bolus dose is defined as administering a bolus dose from the start of a glucose excursion to 1 hour after the start of glucose excursion and before the peak of the glucose excursion. From the plot (Figure 4.1) in Section 4.3.1, if the correct or optimum time to administer a premeal insulin dose is between 1700 and 1800 hours, then an insulin dose between 1800 and 1900 hours will be considered a mistimed bolus dose. Mistimed bolus dose will be calculated and summarized in a table. The definition of a glucose excursion remains the same for an MBD and mistimed bolus dose.

Actual values and change in mistimed boluses doses will be summarized descriptively in a table for each study period and for each week as well. The average value of Weeks 5 and 6 will be used for baseline. Similar statistical analysis will be performed as MBD:

```
proc mixed data = <data>;
    Class StudyPeriod usubjid week;
    Model average_mistimed_bolus_dose = StudyPeriod BaseBMI BaseHbAlc week / ddfm = kenwordroger;
    Random usubjid / subject = usubjid;
    Repeated week / subject = usubjid type = un rcorr;
    Lsmeans StudyPeriod/diff cl pdiff;
run;
```

4.4.1.1.7. Total Insulin Dose per Day, Basal Dose, and Insulin Dose per Type of Meal

The change in insulin doses: basal and mealtime, ratio basal/mealtime, dose per meal as well and total dose in IU/kg, will be calculated and summarized descriptively in a table.

The type of meal will be defined by time intervals: breakfast (0600–1000 hours), lunch (1200–1500 hours), and dinner (1900–2200 hours).

Example SAS Software version 9.4 program code for the MMRM model is as follows:

```
proc mixed data = <data>;
    Class StudyPeriod usubjid week;
    Model Aval = StudyPeriod BaseBMI BaseHbA1c week/ ddfm = kenwordroger;
    Random usubjid / subject = usubjid;
    Repeated week/ subject = usubjid type = un rcorr;
    Lsmeans StudyPeriod/diff cl pdiff;
run;
```

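### The weekly mistimed-bolus count rises when a missed bolus becomes a late one, so the sign of its change does not show whether timing improved

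*SAP*

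**What the plan says.** The secondary objective in SAP 1.1 is "To examine occurrence and change in frequency of mistimed boluses per week between Study Period 1 versus Study Period 2". SAP 4.4.1.1.6 gives this definition of a mistimed dose: "administering a bolus dose from the start of a glucose excursion to 1 hour after the start of glucose excursion and before the peak". It keeps the primary endpoint's definition of a glucose excursion, says "Similar statistical analysis will be performed as MBD", and gives the model statement "Model average_mistimed_bolus_dose = StudyPeriod BaseBMI BaseHbAlc week". The model has no offset or denominator for excursions, meals or boluses given. The weekly scaling (total divided by evaluable CGM days, times seven) is written out only for missed doses, in SAP 4.3.1.1. For mistimed doses it follows from the per-week objective and the shared analysis.

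For the primary endpoint, SAP 4.3.1.1 states: "MBD is defined as no insulin dose from 1 hour prior to through 1 hour after the start of a glucose excursion". The algorithm in the same section is narrower. With no injection in the hour before the nadir, it still adds a missed dose "or if there is an injection before reaching the 70 mg/dL increase but over 30 minutes after the Nt".

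Protocol 2.1.3 gives the hoped-for direction: connected pens may "help reduce missed and mistimed bolus doses". SAP 2.1 reads each test at p ≤ 0.05 without multiplicity adjustment. Neither document plans an analysis that takes missed and mistimed doses together.

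**The concern.** The two endpoints are linked through their definitions. An excursion with no dose within an hour either side of its start is missed. Give the same excursion a dose 20 minutes after its start and before the peak, and it leaves the missed count and enters the mistimed count. Success on the primary endpoint can therefore feed the mistimed count. In the other direction, a participant who stops giving late boluses altogether lowers the mistimed count while doing worse.

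At stake is the reading of a formally tested secondary endpoint. Since fewer mistimed boluses is the expected benefit, a significant rise invites the conclusion that timing got worse, and a fall the conclusion that it got better. Neither follows from the count alone. The Spearman correlations of mistimed doses with TIR, TAR, TBR and HbA1c (SAP 4.4.1.1.9) inherit the difficulty, because a participant who skips most boluses can have few mistimed ones.

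**Working it through.** **The plan's own figure.** Protocol 9.4 gives a difference of 0.323 missed doses per day, SD 0.419, correlation 0.2, two-sided alpha 0.05 and 80% power. Taking 0.419 as the SD within each period, the SD of the difference is 0.419 × √(2 × (1 − 0.2)) = 0.530, and a paired t-test needs N = 24, as in Table 9.1. All 16 cells of that table reproduce on this reading. The weekly effect is 0.323 × 7 = 2.261, matching the protocol's figure of about 2.3. No planning figure is given for the mistimed endpoint.

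**Gross component.** If 2.261 missed boluses per week are recovered, a share s of them is given late, and previously dosed meals keep their timing, the mistimed count changes by 2.261 × s:

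- s = 0.3: 2.261 × 0.3 = +0.68 per week
- s = 0.5: 2.261 × 0.5 = +1.13 per week

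**Bookkeeping.** Protocol 2.1.3 cites an observational study with 5 missed doses per week, assuming 3 meals a day. That gives 21 meals, 16 of them dosed. Assume that 30% of dosed meals are late (not in the documents), and let meals stand in for excursions. Weekly numbers:

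| Scenario | Missed | Late | On time | Missed or late |
|---|---|---|---|---|
| Start | 5.00 | 4.80 | 11.20 | 9.80 |
| A. 2.261 recovered, s = 0.3, other meals unchanged | 2.74 | 5.48 | 12.78 | 8.22 |
| B. 2.261 recovered, all late | 2.74 | 7.06 | 11.20 | 9.80 |
| C. 2.261 recovered, late share of dosed meals falls to 28% | 2.74 | 5.11 | 13.15 | 7.85 |
| D. As A, and late boluses cut by the same 45% (2.261/5) | 2.74 | 3.31 | 14.95 | 6.05 |
| E. One late bolus becomes missed | 6.00 | 3.80 | 11.20 | 9.80 |

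In A and C more meals are dosed on time, yet the mistimed count rises. In E nothing improves, yet it falls. In D it falls by 1.49 because existing late boluses were corrected. With an unchanged late share the rise is 2.261/16 = 14.1%, whatever that share is. The missed-or-late count moves opposite to the on-time number in every row and stays flat in B and E, where on-time dosing is unchanged.

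**Could the gross component reach significance?** Assume the missed-dose SD also applies to mistimed doses: 7 × 0.530 = 3.71 per week. With 50 × 0.65 ≈ 32 evaluable participants, a paired test would give p ≤ 0.05 about 17% of the time for a rise of 0.68 and 39% for 1.13.

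**Overlap between the counts.** Take the nadir as the excursion start, with no dose in the hour before it.

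- A dose at 20 minutes, before the 70 mg/dL rise is reached, is mistimed and not missed.
- A dose at 45 minutes, before the peak, is mistimed under SAP 4.4.1.1.6. The algorithm also calls it missed: if the 70 mg/dL rise came first, under the first condition of step 2.ii.b; if not, under the over-30-minutes condition. That excursion is in both counts.
- A post-peak dose within the hour is neither missed nor mistimed by the text definitions. SAP 4.4.1.1.8 makes it a correction bolus.
- A pre-meal dose plus a top-up before the peak is on time and mistimed, since the mistimed definition does not require that no earlier dose was given.

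**The case against.** Three stronger readings are tempting, and the documents do not support them.

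- *Better adherence will be reported as worse timing.* The SAP never calls a rise worse timing. Its objective is to examine occurrence and change, and its only stated null, for the primary endpoint, is non-directional. The risk is a misreading.
- *The endpoint is biased upward by 0.7 to 1.1 per week.* That range freezes every existing late bolus, whereas advice at Visit 3 may cover late injection timing as well as missed doses (Protocol 4.1.1). If late boluses were cut by the same 45% as missed ones, the net change at a 30% late share would be about −1.5 (s = 0.3) or −0.8 (s = 0.6). At a 10% late share it would be about 0 or +0.6. Even the net sign is unknown.
- *Every excursion is on time, late or missed, so an on-time share should replace the test.* The overlaps shown above break that premise. An on-time share also has its own flaw: a well-timed bolus can prevent the 70 mg/dL rise and so drop out of numerator and denominator. With 5 on time, 4 late and 5 missed, the share is 5/14 = 36%. If two on-time boluses now prevent the excursion, it is 3/12 = 25%. The mistimed MMRM is also specified in Protocol 9.3 and 9.3.2, so removing it would depart from the protocol.

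It is also fair that missed, mistimed and correction boluses are all reported for the same weeks, so a reader can set one beside another. But separate period means do not show how many excursions were missed or late once double counting is removed, and nothing in the plan tells the reader to take the results together.

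**Conclusion.** The point stands in a limited form. By definition, each move from missed to late-before-peak adds one to the tested count and each reverse move removes one, so the sign of the change does not establish whether timing improved. The upward component at the planned effect is 2.26 × s per week, +0.7 to +1.1 for s between 0.3 and 0.5. This rests on an assumed s, and the net change could have either sign. The late share, the SD and the use of meals for excursions are likewise assumptions. The overlap for doses 30 to 60 minutes after the nadir follows from the SAP's wording and needs no assumption beyond taking the nadir as the excursion start. The primary analysis is not affected by how the mistimed count is read. This is one unadjusted secondary endpoint among several, but the repair is small and worth making.

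**What to change.** Keep the protocol-specified mistimed MMRM and add the following to SAP 4.4.1.1.6 before database lock:

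1. Classify each eligible excursion once as on time, late, missed or other. State the precedence rule for three cases: a dose 30 to 60 minutes after the nadir, a post-peak dose within 1 hour, and a pre-meal dose plus a top-up.
2. Tabulate the four categories and the number of eligible excursions by study period.
3. Analyse the weekly number of missed-or-late excursions with the same MMRM, and state that the mistimed change is interpreted only beside it. For a 30-to-60-minute dose before the peak, this count is the same whether the rule calls the excursion missed or late.
4. If an on-time share is shown, keep it descriptive and note that its denominator shrinks when good bolusing prevents excursions.

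The cost is one derived variable from CGM and pen data already processed, one table, one model and a small SAP edit. No planned test is removed, and Protocol 9.3 already allows additional exploratory analyses.

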4.4.1.1.8. Occurrence and Change in Correction Boluses

Correction boluses are defined as taking a bolus dose after the peak of a glucose excursion but within 4 hours from the start of a glucose excursion and prior to start of next glucose excursion.

Actual values and change in correction boluses will be summarized descriptively in a table. Similar statistical analysis will be performed as MBD:

```
proc mixed data = <data>;
    Class StudyPeriod usubjid week;
    Model correction_bolus = StudyPeriod BaseBMI BaseHbAlc week /
    ddfm = kenwordroger;
    Random usubjid / subject = usubjid;
    Repeated week/ subject = usubjid type = un rcorr;
```

Lsmeans StudyPeriod/diff cl pdiff;

run;

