#### 8.1. Effectiveness Assessments

## 8.1.1. Primary Assessments

The primary assessment compares the number of MBDs per week in Study Period 1 and Study Period 2 in participants with T1D or T2D using CGM measurements and CCl data. Missed bolus doses will be determined by the glucose excursion as measured by the CGM.

Missed bolus dose (Figure 8.1) is defined as no insulin dose from 1 hour prior to through 1 hour after the start of a glucose excursion (meal), where a glucose excursion was defined as a >70 mg/dL (>3.9 mmol/L) rise within 2 hours, not preceded by a value <70 mg/dL (<3.9 mmol/L) (Edwards et al. 2021).

[figure not shown]

Figure 8.1. Illustration of missed bolus dose and mistimed bolus.

Using Figure 8.1 as an example, in this study:

- if a dose between 10 and 11 am would be classified as the correct or optimum time to administer the insulin dose, no insulin dose between 10 am and 12 pm would be a MBD; and
- if a dose between 5 and 6 pm would be classified as the correct or optimum time to administer the insulin dose before the meal, an insulin dose between 6 and 7 pm is defined as a mistimed bolus dose.

Sy et al. (2022) provides a graphical representation of several days of CGM data with various meal bolus situations.

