## 8.1.2. Secondary Assessments

Study IORW will have secondary measures as described in Table 3.1.

The study will evaluate the change in percentage TIR, TAR, TBR, mean sensor glucose coefficient of variation between Study Period 1 and Study Period 2 in participants with T1D or T2D using CGM and CCl data. The glucose TIR for this analysis is ≥70 and ≤180 mg/dL.

In addition, the occurrence and change in mistimed bolus will be evaluated (Figure 8.1). A mistimed bolus dose is defined as a bolus dose administered from the start of a glucose excursion (meal) up to 1 hour after the start of glucose excursion and before the peak of glucose excursion.

Change in correction boluses from masked to unmasked period will also be evaluated. Correction bolus is defined as taking a bolus dose given after the peak of a glucose excursion but within 4 hours from the start of a glucose excursion and prior to start of next glucose excursion.

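### When two excursions start less than 5 hours apart, the correction-bolus rule also counts the on-time bolus for the second meal, so the change between periods cannot be read as corrective behaviour

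*SAP*

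**What the plan says.** Three dose labels hang on the start of a glucose excursion.

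- **Correction.** SAP 4.4.1.1.8 defines it as a bolus after the peak of an excursion that falls "within 4 hours from the start of a glucose excursion and prior to start of next glucose excursion". Protocol 8.1.2 ("Correction bolus is defined as taking a bolus dose given after the peak of a glucose excursion") and Protocol 9.3.2 carry the same rule.
- **On-time meal dose.** In the worked example of SAP 4.3.1.1, a "dose between 1000 and 1100 hours would be classified as the correct or optimum time to administer the insulin dose before" the 11:00 meal. Protocol 8.1.1 uses the same hour. The missed-dose algorithm agrees: "If there is an injection within 1 hour prior to Nt, then move to the next nadir".
- **Mistimed.** SAP 4.4.1.1.6 defines this as "administering a bolus dose from the start of a glucose excursion to 1 hour after the start of glucose excursion", provided the dose comes before the peak.

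Neither document makes the labels mutually exclusive, sets an order of precedence, or uses meal entries to separate a meal dose from a correction. SAP 4.4.1.1.7 assigns doses to meals by clock time: breakfast 06:00 to 10:00, lunch 12:00 to 15:00, dinner 19:00 to 22:00. It gives no window for snacks.

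Correction boluses are a secondary endpoint. They are compared between periods with the same type of mixed model as missed doses, at p ≤ 0.05 without multiplicity adjustment (SAP 2.1).

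**The concern.** The correction window stays open until the next excursion starts. The on-time window is the hour that ends at that same moment. When the first excursion is recent enough, the two windows share time, and an injection in the shared part carries both labels.

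This matters because Study Period 2 is meant to change timing. Protocol 4.1.1 names missed doses and late injections among the topics on which the healthcare professional may advise. A dose moved from just after a meal's start to just before it can leave the mistimed count and enter the correction count. A missed dose that is now taken on time can add a correction. In neither case has the participant corrected anything. The Period 2 minus Period 1 change would then mix corrective dosing with better meal dosing.

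The correction doses listed in the insulin-dose endpoint (Protocol Table 3.1) share the ambiguity. Suppose excursions start at 08:30 (peak 09:45) and 12:30. A dose at 12:15 is a lunch dose by the clock rule and a correction by SAP 4.4.1.1.8.

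**Working it through.** **Plan's own figures.** The documents give none for correction boluses. The only figure used here is the planned effect on missed doses: 0.323 per day × 7 = 2.26, stated as about 2.3 per week (Protocol 9.4).

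**Example.** Excursions start at 08:30 (peak 09:45) and at 12:00. The 4-hour limit from the first start is 12:30.

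- Dose at 11:45: after the first peak, 3 h 15 min after the first start, before the second start. It is a correction. It is also 15 minutes ahead of the second start, so it is on-time.
- Dose at 12:15: still within 4 hours of 08:30, but after the second start. It is not a correction. It is within an hour of the second start and, if the second peak has not yet come, it is mistimed.

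Moving the dose 30 minutes earlier lowers mistimed by one and raises corrections by one.

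**General condition.** Let G be the gap between the two starts, x the lead of the dose before the second start (more than 0, up to 1 h), and p the time from the first start to its peak. The dose carries both labels when

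p + x < G ≤ 4 h + x.

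With x at most 1 h, overlap needs a gap below 5 h, apart from the boundary instant. For gaps from 4 to 5 h, the share of the on-time hour that overlaps is 5 − G: 100% at 4 h, 75% at 4.25 h, 50% at 4.5 h, 25% at 4.75 h, 0% at 5 h. Between 3 and 4 h it is 100% if the first peak comes within 2 h. The documents define no peak time.

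**How often (illustration).** Assume that starts are independent and uniform over the SAP's meal windows, and that the earlier meal produces an excursion.

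- Breakfast to lunch: the gap is at least 2 h, and for g up to 5 h, P(G ≤ g) = [(g − 2)²/2] / (4 × 3) = (g − 2)²/24.
- Lunch to dinner: the gap is at least 4 h, and for g up to 7 h, P(G ≤ g) = [(g − 4)²/2] / (3 × 3) = (g − 4)²/18.

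| Lead | Limit on gap | Lunch bolus overlaps | Dinner bolus overlaps |
|---|---|---|---|
| 15 min | 4.25 h | 2.25²/24 = 21.1% | 0.25²/18 = 0.3% |
| 60 min | 5 h | 3²/24 = 37.5% | 1²/18 = 5.6% |

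These figures ignore the need for the first peak to have passed. With that peak at 2 h, the lunch figures become 21.1% − 0.25²/24 = 20.8% and 37.5% − 1²/24 = 33.3%. At zero lead there is no overlap, because a dose at the start is not before it.

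**Effect on the period contrast.** Assume that 2.3 missed doses per week become on-time doses, spread equally over three meals, with no excursion close enough before breakfast to matter.

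- 15 min lead: 2.3 × (0 + 0.211 + 0.003)/3 = 0.16 per week.
- 60 min lead: 2.3 × (0 + 0.375 + 0.056)/3 = 0.33 per week, or 2.3 × (0 + 0.333 + 0.056)/3 = 0.30 with the first peak at 2 h.

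Each further 10% of these doses falling in the overlap adds 2.3 × 0.10 = 0.23 per week. Snack excursions would shorten the gaps, and doses that move from mistimed to on-time would add to the count. The documents give no figure for either.

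**The case against.** The strongest reply is about direction. A false correction needs an earlier excursion of more than 70 mg/dL. Earlier and fewer missed doses may remove some of those excursions, and with them both false and true corrections. A reader might infer that the endpoint is biased upward overall. The documents do not support that: only the mislabelled part is known to rise with better timing, other things equal.

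Size is also easily overstated. Multiplying 21% by seven days gives about 1.5 false corrections per week from lunch. That is a level of mislabelling, and it requires a breakfast excursion, a lunch excursion and an on-time lunch dose every day. On-time doses already taken in Period 1 are mislabelled in both periods and, other things equal, cancel. The SAP's windows are labels for typing doses, not observed mealtimes, and drawing breakfast and lunch independently allows 10:00 followed by 12:00. High rates for dinner after a snack would need a snack window that neither document gives.

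A reader might also fear that a rise would be taken for poorer control or insulin stacking. That is speculative, since time in, above and below range and sensor-detected hypoglycaemia are reported alongside.

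The remedy has a weakness too. If an on-time dose works so well that no excursion follows, there is no next start, and the dose still counts as a correction. Excluding only doses followed by an excursion could itself make the count rise as meals are better covered.

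These points limit the claim and shape the remedy. None of them justifies counting as a correction a dose that the plan itself calls on-time.

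**Conclusion.** The overlap follows from the definitions alone and needs no assumption. It arises only when the second excursion starts less than 5 hours after the first and the first peak has passed. Under uniform meal timing it affects a fifth to somewhat over a third of on-time lunch boluses and few dinner boluses. Its contribution to the period contrast is about 0.16 to 0.33 per week, on the stated assumptions about meal timing, preceding excursions and the planned 2.3 missed doses per week, and before snacks or mistimed-to-on-time shifts.

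The change in correction boluses therefore cannot be read as corrective behaviour. The net direction of the endpoint is not derivable. The missed-dose endpoint and its sample size do not use this rule and are unaffected. The point is worth fixing because the endpoint is formally compared between periods and the repair is cheap.

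**What to change.** Before database lock, make the dose classes mutually exclusive, with the on-time class taking precedence. A correction is then a bolus after the peak of an excursion, within 4 hours of its start, and more than 1 hour before the start of the next excursion. This removes the overlap with the on-time hour at every gap. State also that one injection may not be counted under both a meal type and correction in the insulin-dose summaries.

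Report the count under the present rule alongside, so that readers can see how much depends on the definition. Add a supportive count limited to correction doses given at sensor glucose above 180 mg/dL, the trial's own limit for time above range. This addresses well-covered meals with no following excursion. State that it reduces this residual and does not remove it, since an effective meal dose may also be given above 180 mg/dL.

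The cost is SAP wording and a few lines of derivation code, with no new data. The downside is that a genuine correction taken in the hour before the next excursion is classed as a meal bolus. Fixing the rule before lock keeps the choice independent of the results, in line with the SAP's own freeze on the missed-dose algorithm (4.3.1.1).
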